6.0 Data and Specimen Banking

If this study does not involve data or specimen banking for future use, type "N/A" and delete the sub-headings below. Otherwise, complete all items below.

1. Storage and Access: Data will be stored on secure, password-protected Fairview Health Services Servers.
2. Data: BP control history and relevant cardiovascular and side-effect data will be collected. We will not be banking any of this information for other studies, this is for the present study only.
3. Release/Sharing: No individual data or patient information will be released or shared with any individual who is not approved to participate in this research study.

7.0 Sharing of Results with Participants

1. We will share patient's genetic results, if requested. None of the genes are known to be major cancer causing genes. If we share the genetic results with the patient this will be done by a Fairview clinician on our research team. We will offer genetic counseling services, if the patient requests such a service. The laboratory where the genetic testing is performed (the University of Arizona Genomics core) is a CLIA-certified genetic laboratory.

8.0 Study Duration

1. *Describe:*
 - An individual will just need to provide two buccal swabs and complete a BP medication survey. This will take less than one hour.
 - We anticipate it will take approximately 6 months to recruit our subjects.
 - We anticipate it will take one year in total from beginning of study for data to be presented in abstract for and submitted as a manuscript.

9.0 Study Population

1. Inclusion Criteria:
 1. Subject is able and willing to provide informed consent
 2. Subject is ≥ 20 and ≤ 85 years of age

PROTOCOL TITLE:

VERSION DATE:

3. Subject with diagnosis of Hypertension for a minimum of 1 year
4. Subject has been on the same class/classes of blood pressure medication for a minimum of 6 months. Note: A change in dosage, frequency, or specific medication is acceptable as long as there have been no changes to the class/classes of medications prescribed.
5. Subject with a Body Mass Index (BMI) ≥ 19 and ≤ 45
6. Subject is currently prescribed and taking one of the following classes of medications alone or in combination with each other.
 - o Diuretics (thiazide or thiazide-like)
 - o ACE Inhibitors
 - o Angiotensin Receptor Blocker (ARB)
 - o Beta-blockers
 - o Ca+ Channel Blockers

2. Exclusion Criteria:

1. Subject has a diagnosis of secondary hypertension or is experiencing a complication of pregnancy.
2. Subject is currently prescribed and taking any additional class of medication(s) for high blood pressure not included in the list above
3. Subject has Systolic BP > 190 or Diastolic BP > 120 documented within the six months prior to visit.
4. Any other reason that the subject is inappropriate for study enrollment in the opinion of the Investigator.

2. Screening:

Because this is a retrospective chart review study, subjects will be screened by a Fairview employee (or AHC personnel) for eligibility. Only subjects who have opted in (or who have not opted out) of research will be contacted.

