3.0 Study Endpoints/Events/Outcomes

1. Primary Endpoint/Event/Outcome:

To assess the effectiveness of the use of a patient’s genes to predict which hypertension therapy is successful, as measured by:

1. Level of blood pressure control (<140/<90)
2. Change in blood pressure from baseline to control

2. Secondary Endpoint(s)/Event(s)/Outcome(s):

Blood Pressure control with respect to:

1. Number of medications needed to obtain control
2. Time to control
3. Number of office visits to control
4. Side effects from hypertension therapy
5. Hypertension associated adverse events during the course of treatment

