- Review Inclusion/Exclusion Criteria. The investigator and/or designee will review all criteria to determine if the subject is eligible for enrolment. Eligibility of all subjects must personally be confirmed by the Investigator and will be documented on the CRF.

Enrollment

- Assign Identification Number to Eligible Subjects.

Chart Review

- Record demographics, antihypertensive medical history and most recent blood Pressure. Data will be documented in the source document and recorded on the patient demographic form, including but not limited to the following:
 - Age
 - Sex

PROTOCOL TITLE:

VERSION DATE:

- Height
- Weight
- Race
- Ethnicity

(additional data for collection is included in the attachment entitled "metrics")

Specimen Collection

- Collect Buccal Specimen.

Subject Numbering

Subjects meeting the criteria for enrollment (and their specimens) will be identified by unique numbers that will be assigned sequentially by order of enrollment. The pre-assigned investigational site number will be prefixed with GCE and the identification number and separated by a hyphen (e.g., GCE-001etc.). Throughout the descriptions within the protocol the A swab will be referring to the swab that has originated from the right cheek, while the B swab will be that that has originated from the left cheek. To further clarify. Subject GCE-001 will be given two barcoded tubes. These barcode numbers should be recorded for each patient. These will also be recorded as originating from the right cheek (A) or left cheek (B).

At no time should any study paperwork or specimens be marked with the subject's name or any other traceable identifier except for the informed consent form, which is signed by the subject and kept at the site. At no time should the original (signed) or a copy of this form be collected by the Sponsor or its representative.

2. Follow-Up: Data will be collected for up to one year.

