16.0 Data Management

1. Data Analysis Plan:

The Investigator is responsible to ensure the accuracy, completeness, and timeliness of reported data.

PROTOCOL TITLE:

VERSION DATE:

All data will be compiled within the Fairview system on secure servers. De-identified final data may be sent to Geneticure using a secure, password-protected Excel spreadsheet on a server that is only accessible to IRB-approved personnel and is fully auditable. The database will be validated prior to use in the study. All required data will be recorded on CRFs or paper facsimiles. Data collected within the CRFs will be supported by source documents as appropriate and may be updated to reflect the latest observations on the subjects participating in the study. Corrections to the source documentation will be made in a manner that does not obscure the original entry and will be dated and initialed by the Investigator or assigned designee. It is important for data entry to occur in a timely manner, therefore, data collected on source documents should be transferred into CRFs as soon as possible following study visits.

All data will be coded for statistical analysis (i.e. drug classes will be coded numerically and genotypes will be coded numerically). Subject's raw genetic data will be entered into the Geneticure for Hypertension algorithm. All data will be analyzed with SPSS v.20. Normality of the data will be assessed using Levene's test prior to statistical analysis and any correction for non-normal data distribution will be used. Descriptive statistics will be computed (average time for blood pressure control, average number of visits to the clinician for blood pressure control, age, height, weight, BMI, etc.).

Data will be initially analysed following the collection of samples/data from up to 600 subjects. Statistical tests will be corrected for the number of tests run (preservation of alpha). Ordinary least squares regression via univariate modelling will be used to estimate the magnitude of linearity between drug class that yielded the best blood pressure control and genetic profile of the subject. Multiple regression analysis will be performed to determine the impact of confounding variables (height, weight, age, race) on blood pressure control. For all statistical analyses an alpha level of 0.05 will be used to determine statistical significance.

Missing Data

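### Eligibility neither ties listed drugs to hypertension nor screens out other BP-lowering drugs given for other reasons, so class, medication count and BP response can be misattributed

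*Combined protocol and SAP*

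**What the plan says.** Section 9.0 defines the eligible drug exposure in three places.

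- Inclusion criterion 6: "Subject is currently prescribed and taking one of the following classes of medications alone or in combination with each other". Five classes follow (thiazide or thiazide-like diuretics, ACE inhibitors, ARBs, beta-blockers, calcium channel blockers). No indication is stated.
- Exclusion criterion 2: "Subject is currently prescribed and taking any additional class of medication(s) for high blood pressure not included in the list above". Here an indication is stated.
- Inclusion criterion 4: "Subject has been on the same class/classes of blood pressure medication for a minimum of 6 months".

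Three outcomes or analysis variables depend on that exposure.

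- Section 16.0 regresses the relation "between drug class that yielded the best blood pressure control and genetic profile of the subject".
- Section 3.0 has a primary endpoint, "Change in blood pressure from baseline to control", and a secondary endpoint, "Number of medications needed to obtain control".
- The only adjustment is a multiple regression in Section 16.0 to "determine the impact of confounding variables (height, weight, age, race) on blood pressure control".

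For data capture, Section 5.0 says to "Record demographics, antihypertensive medical history and most recent blood Pressure" and refers to a metrics attachment for further items. That attachment and the BP history survey are not part of the public document.

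**The concern.** Several of the listed classes have uses other than hypertension, and several BP-lowering drugs lie outside the list. A hypertensive patient may take a beta-blocker for angina or arrhythmia, or an alpha-blocker for prostate symptoms. (These are illustrations; the documents do not discuss them.) In the first case the class was chosen because of another disease, so its presence is weak evidence that it was the class that worked for BP. In the second, part of the BP response comes from a drug that the analysis does not see.

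This matters more here than in a trial with assigned treatment. The Study Summary and Section 4.0 describe a population that has already reached control, so control status varies little. The class and the number of drugs then carry much of the information on which therapy succeeded. If those variables partly reflect comorbidity, the class-genotype comparison and the medication count no longer measure only what the objectives ask. Beta-blockers are a listed class and also the subject of the beta-1 receptor example in the power section.

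**Working it through.** No figure in the documents tests this point, so the check is a reading of the eligibility text against the analysis text.

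**Step 1. Apply the criteria as written.** Take three patients, each with hypertension diagnosed for at least a year, on unchanged classes for six months, and otherwise eligible.

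| Patient | Meets inclusion 6 | Removed by exclusion 2 | Listed classes taken | Classes charted for hypertension | All BP-lowering classes taken |
|---|---|---|---|---|---|
| A: ACE inhibitor for hypertension, beta-blocker for angina | Yes | No | 2 | 1 | 2 |
| B: ACE inhibitor for hypertension, alpha-blocker for prostate symptoms | Yes | No | 1 | 1 | 2 |
| C: one beta-blocker, for both hypertension and angina | Yes | No | 1 | 1 | 1 |

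All three are eligible. A and B satisfy inclusion 4 even on its narrowest reading, because the ACE inhibitor alone is a stable blood pressure medication.

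**Step 2. Follow each patient into the analysis.**

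- *Class.* For A, nothing says whether the credited class is the ACE inhibitor, the beta-blocker or the pair. For B, the ACE inhibitor is the only listed class that can be credited. For C, the label is correct.
- *Count.* The three right-hand columns are three possible counts. They differ for A (2, 1, 2) and B (1, 1, 2) and agree for C. Section 3.0 gives no counting rule. The possible error runs both ways: counting every listed drug may overstate what A needed, and counting only listed or hypertension-charted drugs may understate what produced control in B.
- *BP response.* In B, the change from baseline to control can include the alpha-blocker's effect. In A, it can include the beta-blocker's effect, depending on whether that drug was started before or after baseline.

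**Step 3. Look for a correction elsewhere.**

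- The covariates in Section 16.0 are height, weight, age and race. Indication, comorbidity and other BP-lowering drugs are absent.
- The disease-specific exclusions in Section 9.0 are secondary hypertension and a complication of pregnancy. Neither removes A or B.
- Exclusion 4 leaves other exclusions to the investigator's opinion. Section 13.0 permits, but does not require, withdrawal for a severe co-morbidity. Neither is tied to indication.
- Section 11.0 expects co-morbidities and gives them as a reason to consent up to 2000 people.

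Nothing in the plan as written says how indication is established, how drugs with another or a double indication are classed and counted, or how unlisted BP-lowering drugs are handled.

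**The case against.** The best defence is that the protocol consistently means hypertension treatment. Inclusion 4 speaks of blood pressure medication, Section 5.0 of antihypertensive history and BP medication history, and Section 8.0 of a BP medication survey. Every patient has diagnosed hypertension, so a listed drug may serve both purposes and be labelled correctly, as in patient C. The metrics attachment and the survey may already record indication. Investigator discretion and withdrawal may remove some cases, and the allowance for co-morbidities in Section 11.0 can be read as a plan to lose such patients rather than analyse them.

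Much of this stands. It means that misattribution can occur, not that it has been shown to occur, and the data field may already exist. It does not close the gap. Wording that suggests intent is not a rule for classing or counting, the safeguards are discretionary, and Section 16.0 makes no use of indication even if it is collected.

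Two stronger readings are tempting and should be resisted.

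- *A fixed loss of effect.* A reader might assume that 10–30% of a class's users take it for another reason and show no genotype effect. The WNK-1 contrast in Section 16.0 (100.8 − 97.6 = 3.2 mmHg) would then shrink to 3.2 × 0.9 = 2.88 or 3.2 × 0.7 = 2.24 mmHg, and the required sample would grow by 1/0.9² = 1.23 to 1/0.7² = 2.04 times. The documents support neither assumption. They give no rate, and a patient taking the drug for another reason is still exposed to it, so nothing suggests that the genotype effect vanishes. That arithmetic also concerns mean pressure by genotype among users of a drug, whereas selection by comorbidity bears mainly on the class-genotype regression.
- *A count overstated by one in every affected patient.* Patients B and C show that this does not hold for unlisted or dual-purpose drugs.

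**Conclusion.** The point holds in conditional form. Applied exactly as written, the eligibility criteria admit patients whose listed class was chosen for another disease, or whose BP is partly lowered by a drug outside the list, and the planned covariates do not correct for either. Class, medication count and BP response can be misattributed in those patients.

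The size cannot be stated. It depends on the share of such patients and on how far the other drug contributed to control, and the documents give neither. The direction is not fixed: the count can err either way, and the credited BP response depends on when the other drug was started.

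The conclusion assumes that the unseen attachment and survey do not already capture indication and other BP-lowering drugs. If they do, the remaining gap is in the analysis plan alone. The point is worth settling before chart abstraction begins, because a field left out then means reopening charts.

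**What to change.** No patient's treatment is affected; the changes concern abstraction and analysis.

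1. At chart abstraction, record the charted indication of each listed drug as hypertension, other or both. Where the chart is silent, code it as not stated rather than guess.
2. Record any other BP-lowering drug, whatever its indication. If the metrics attachment already collects items 1 and 2, use those fields and say so.
3. Keep all patients. Define a flag for a listed drug with a non-hypertension indication or for any other BP-lowering drug, and add it as a covariate in the Section 16.0 models.
4. Repeat the class-genotype and medication-count analyses without flagged patients, labelled in advance as sensitivity analyses.
5. Report the medication count both ways: all BP-lowering drugs, and only those charted for hypertension. Simply dropping drugs given for other reasons would ignore their BP effect and recreate the misattribution in the other direction.

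The cost is one or two abstraction fields and a smaller sample in the restricted analyses. Section 16.0 allows for 70% retention of up to 2000 recruits, or 2000 × 0.70 = 1400 if recruitment is full, against the 600 that Section 11.0 calls ideal. That suggests room overall, but the documents give no class-specific numbers, so the precision of a restricted comparison within one class cannot be promised.

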10.0 Vulnerable Populations

1. Vulnerable Populations:

- Children
- Pregnant women/Fetuses/Neonates
- Prisoners
- Adults lacking capacity to consent and/or adults with diminished capacity to consent, including, but not limited to, those with acute medical conditions, psychiatric disorders, neurologic disorders, developmental disorders, and behavioral disorders
- Approached for participation in research during a stressful situation such as emergency room setting, childbirth (labor), etc.

PROTOCOL TITLE:

VERSION DATE:

- Disadvantaged in the distribution of social goods and services such as income, housing, or healthcare
 - Serious health condition for which there are no satisfactory standard treatments
 - Fear of negative consequences for not participating in the research (e.g. institutionalization, deportation, disclosure of stigmatizing behavior)
 - Any other circumstance/dynamic that could increase vulnerability to coercion or exploitation that might influence consent to research or decision to continue in research
 - Undervalued or disenfranchised social group
 - Members of the military
 - Non-English speakers
 - Those unable to read (illiterate)
 - Employees of the researcher
 - Students of the researcher
 - None of the above
2. *Adults lacking capacity to consent and/or adults with diminished capacity to consent:*
- N/A
3. Additional Safeguards: *If the research involves individuals Checked in Section 10.1 above, provide justification for their inclusion and describe additional safeguards included to protect their rights and welfare.*
- N/A

11.0 Local Number of Participants

1. Local Number of Participants to be Consented: Up to 2000 subjects may participate in the study. 600 subjects are ideal for statistical analysis but given possible co-morbidities, we aim to consent up to 2000 individuals.

12.0 Local Recruitment Methods

1. Recruitment Process: Subjects will be recruited via letter, phone call, and e-mail (drafts of each are attached to the IRB ETHOS “smart” form)
2. Source of Participants: Medical record review
3. Identification of Potential Participants: Recruited based on inclusion/exclusion criteria, Fairview participation, and willing to participate in a research study. Participants will primarily be identified via AHC-CTSI data that is gathered daily for Fairview participants

PROTOCOL TITLE:

VERSION DATE:

who have not opted-out of research. In addition, we may also use the following reach-out methods:

- [name] is a Fairview clinician
- [name] via mailer.
- In the mailer (attached to the IRB) we ask the patient regarding approval of use of medical records. In addition to this we will not use any patient who has opted out of research within the Fairview system.

4. Recruitment Materials: Attached
5. Payment: 30 dollars for completion of the buccal collection and BP history survey (which is attached)

13.0 Withdrawal of Participants

1. Withdrawal Circumstances: The researchers may withdraw a subject if they have inadequate DNA yield, they have a severe co-morbidity that was not previously flagged, or if the participant does not submit their buccal swab.
2. Withdrawal Procedures: If a participant withdraws no data will be gathered after this time and no data from this participant will be used in the research. It is the patient's right to withdraw at any time.
3. Termination Procedures: N/A

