The blood pressure panel created by Geneticure has been created to comprehensively assess seventeen common genetic variants in the liver (drug metabolizing enzyme) cardiac, vascular, and renal systems that can improve therapeutic guidance for the clinician based on known functional alterations of the protein through these genetic changes, as well as demonstrated effects of certain drug classes on these various genotypes. Based on this information, a clinician can guide therapy with knowledge specific to their patient, rather than “trial-and-error” based on population data and using drugs with least side effects initially.

1. Preliminary Data: N/A
2. Existing Literature:

Background

Hypertension (high blood pressure) is one of the most important preventable contributors to disease and death in the United States and represents the most common condition seen in the primary care setting^{1,2}. According to the American Heart Association, approximately 78 million adults (1 in 3) living in the United States have hypertension with more than 5 million new diagnoses made each year^{3,4}. Of these individuals, 82% are aware they have it, 75% are currently being treated for it, but only 52% have their blood pressure under control (thus, ~48% do not have adequate blood pressure control). Hypertension is known to lead to myocardial infarction, stroke, renal failure, and death if not detected early and treated appropriately. In fact, in 2009, high blood pressure was listed as a primary or contributing cause of death in ~350,000 of the ~2.4 million U.S. deaths (14% of all deaths). From 1999-2009 the number of deaths attributable to hypertension increased by 44%. In 2009, the direct and indirect economic burden on the United States health care system associated with hypertension was

PROTOCOL TITLE:

VERSION DATE:

estimated at \$51 billion. With the advent of improved diagnostic techniques, increased rates of health care utilization and screening, and the increasing age of the population, a continual upward trend in this expenditure is expected. Because nearly two-thirds of the people living with hypertension worldwide reside in developing countries, providing optimal treatment at the lowest cost is critically important.

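### Section 13.0 lets researchers withdraw enrolled subjects for an undefined severe co-morbidity, which can selectively remove patients who have the adverse-event endpoint

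*Combined protocol and SAP*

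**What the plan says.** Section 13.0 gives three grounds on which the study team may remove someone: too little DNA, that "they have a severe co-morbidity that was not previously flagged", or failure to return the swab. The next item, on procedures, says that once a participant withdraws, collection stops and "no data from this participant will be used in the research". It describes no other handling of data.

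Section 9.0 names two medical conditions as exclusions: "Subject has a diagnosis of secondary hypertension or is experiencing a complication of pregnancy". Blood pressure, BMI, age and drug-class limits are listed separately. There is also an open clause: "Any other reason that the subject is inappropriate for study enrollment in the opinion of the Investigator". That clause concerns enrolment and names no condition.

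Section 3.0 lists as its fifth secondary endpoint "Hypertension associated adverse events during the course of treatment", without defining the events. The section 2.0 background states: "Hypertension is known to lead to myocardial infarction, stroke, renal failure, and death if not detected early and treated appropriately".

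In the section 5.0 general flow, consent and swab are returned at step 3, the swab goes for genotyping at step 4, and charts are abstracted at step 6. Blinding is stated for genotyping only. Section 16.0 analyses whoever has data and rules out sensitivity analyses for missing data.

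**The concern.** A withdrawal rule is harmless if it cannot depend on the outcome. This one can. The triggering condition is undefined, it may be discovered in the same chart that holds the outcomes, and the people deciding are not required to be unaware of blood pressure response, drug class or events. Blinded genotyping does not address selection on the outcome.

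If a stroke on treatment is read as a previously unflagged severe co-morbidity, the patient leaves the study and, on the natural reading of section 13.0, the event leaves with them. Endpoint 5 would then be estimated in a cohort from which some of its own events had been removed. No planned analysis or report would reveal how many.

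**Working it through.** The plan states no figure for this rule, so the main check sets the provisions side by side. The arithmetic that follows is illustrative.

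**Textual check**

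1. *Is the condition defined?* No. Section 9.0 names secondary hypertension and a complication of pregnancy, and its open clause lists nothing. Section 13.0 refers to no list.
2. *Can it be found after enrolment?* Yes. Abstraction is step 6, after consent and swab return (step 3) and dispatch for genotyping (step 4).
3. *Is the decision shielded from outcome?* No such provision is stated.
4. *Can the condition be an endpoint event?* Plausibly. The background's named consequences of hypertension are severe conditions, and endpoint 5 is undefined, so nothing separates the two.
5. *Would the loss be visible?* No. Reporting of withdrawals by reason is not required, and section 16.0 excludes missing-data sensitivity analyses.

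**Room for removals**

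Section 11.0 says "600 subjects are ideal for statistical analysis but given possible co-morbidities, we aim to consent up to 2000 individuals". At the 70% retention in section 16.0, 600 analysed subjects need 600/0.70 = 857.1, so 858 consented. Going from 2000 to 600 keeps 600/2000 = 30%, a loss of up to 70%. Co-morbidity is thus an expected reason for loss, but the documents do not say how much of it would occur as withdrawal under 13.0.

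**Illustration for endpoint 5**

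Assumptions, none from the documents: true event risks of 10% and 5% in two groups (also 6% and 3%); a share r of event patients withdrawn and dropped; nobody else removed; a two-sided two-proportion test at alpha 0.05. The plan names no test for this endpoint. The 300 per group before removals is from section 16.0.

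Observed risk = p(1 − r)/(1 − pr). For p = 10% and r = 50%: 0.05/0.95 = 5.3%. For p = 5%: 0.025/0.975 = 2.6%.

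Power = Φ[(d − 1.96·SE0)/SE1], where d is the difference in observed risks and SE0 and SE1 are its pooled and unpooled standard errors.

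| Share of event patients dropped | Observed risks (true 10% vs 5%) | Power | Power (true 6% vs 3%) |
|---|---|---|---|
| 0% | 10.0% vs 5.0% | 64% | 43% |
| 25% | 7.7% vs 3.8% | 53% | 34% |
| 50% | 5.3% vs 2.6% | 39% | 24% |
| 75% | 2.7% vs 1.3% | 22% | 15% |

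At 100% no events remain.

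The observed odds are p(1 − r)/(1 − p). Equal r in both groups therefore leaves the odds ratio unchanged, while the risks, the risk difference and the power all shrink. Unequal r biases it: with 10% true risk in both groups (odds ratio 1.0), dropping 50% of event patients in one group and 25% in the other gives an odds ratio of 0.50/0.75 = 0.67.

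**The case against.** Several points on the other side are fair.

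- *The discard sentence may not apply.* It is conditioned on the participant withdrawing, and the next sentence concerns the patient's right to withdraw. Extending it to researcher-initiated withdrawal is an inference. That stands. But it is the only procedure given, and if it does not apply, the protocol does not say what happens to these subjects' data.
- *Late discovery is possible, not prescribed.* The detailed procedures in section 5.0 put eligibility review and investigator confirmation before chart review, and section 13.0 sets no timing. That also stands: the text permits withdrawal after outcomes are seen but does not direct it. Because the study is retrospective, outcomes are already in the chart at screening, so an earlier decision alone is not a full remedy.
- *Section 9.0 already allows discretion.* Its investigator-opinion clause does so at enrolment, and section 13.0 could be read as late application of it. That explains the clause but does not define it.
- *The overlap with endpoint 5 is not documented.* The background list is general, and the endpoint has no components. The overlap is plausible, no more.
- *An attachment on metrics is not available.* It might list co-morbidities, though section 13.0 does not point to it.

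A reader might go further and infer that the rule removes poorly controlled patients and so distorts the primary blood pressure comparison. The documents do not support that. The rule concerns co-morbidity, not pressure; sections 4.0 and the study summary describe patients with a history of control; and genotyping is blinded and done at an outside facility, away from the chart reviewers. Nothing suggests that the highest pressures in one genotype group would be singled out.

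**Conclusion.** The point holds for secondary endpoint 5. As written, section 13.0 permits undefined, unblinded, post-enrolment withdrawal that can take endpoint events out of the analysis without trace. This rests on two readings: that the discard sentence covers researcher-initiated withdrawals, and that a serious hypertension-related event could be judged a severe co-morbidity. Both are plausible, and neither is stated.

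The size cannot be determined. The tabulated figures show direction and sensitivity under assumed rates; they are not estimates for this study. Unequal removal between genotype groups is less likely if those deciding do not know the genotype, but the protocol does not require that they be kept unaware. No claim is made about the primary endpoints. The flaw should be corrected because it is avoidable at little cost.

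**What to change.** - Remove post-enrolment withdrawal for co-morbidity from section 13.0. Alternatively, restrict it to conditions pre-listed in section 9.0 that are not themselves events under endpoint 5, applied before genotype is linked and without regard to blood pressure response or events.
- Limit the rule that no data are used to participants who revoke consent.
- For researcher-initiated co-morbidity withdrawals with a usable genotype, keep the abstracted data in the analysis. Subjects with no swab or inadequate DNA cannot enter a genotype association and are unaffected.
- Report the numbers withdrawn by reason. If wanted, add a sensitivity analysis that excludes the co-morbidity withdrawals.

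The cost is a change of protocol wording, a slightly more heterogeneous sample and minor extra reporting.
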